4.4 Definition of variables

4.4.1 Primary outcome variables

Dependent variables

- Presence of signs and symptoms of OIWS
 - According to daily evaluation by investigator after an episode of opioid weaning has begun (See Appendix III)

Independent variables

- **Presence of OIWS** (qualitative nominal - dichotomous)
 - According to DSM-5 evaluation completed daily by physician after an episode of opioid weaning has begun
- **Demographic and clinical variables**
 - **Age** (quantitative continuous): Age in years at ICU admission
 - **Sex** (qualitative nominal - dichotomous)
 - **Weight** (quantitative continuous): Weight in kg at ICU admission
 - **Height** (quantitative continuous): Height in cm at ICU admission
 - **Body mass index (BMI)** (quantitative continuous): In kg/m² at ICU admission
 - **Ethnicity** (qualitative nominal)
 - **Site of ICU admission** (qualitative nominal - dichotomous)
 - **Smoking status** (qualitative nominal - dichotomous)
 - Number of cigarettes per day according to medical chart, patient or family at ICU admission (quantitative discrete)
 - Number of pack-years according to medical chart, patient or family at ICU admission (quantitative continuous)
 - **Principal diagnosis at ICU admission** (qualitative nominal)
 - Definite diagnosis according to medical chart at ICU admission using ICD-10 classification
 - **Length of stay in the ICU** (quantitative continuous)
 - Time in hours from ICU admission to ICU discharge, transfer to ward or patient death, according to medical chart
 - Opioid withdrawal has been associated with longer ICU stays (4-6)
 - **Duration of mechanical ventilation** (quantitative continuous)

- Time in hours according to medical chart
- Longer duration of mechanical ventilation has been associated with increased risk of IWS in ICU patients (7)
- **Acute Physiology and Chronic Health Evaluation II Score (APACHE II)** (qualitative ordinal)
 - To assess severity of disease and ICU mortality on a scale of 0 to 71 (47)
 - As reported by an archivist based on data from the first 24 hours of ICU admission
- **Glasgow Coma Scale (GCS)** (qualitative ordinal)
 - To assess mental status and severity of brain injury on a scale of 3 to 15 (48)
 - As reported by nurse on patient flow sheet at ICU admission
- **Renal function**
 - Daily serum creatinine in $\mu\text{mol/L}$ according to medical chart (quantitative continuous)

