5.1 Statistical analysis

5.1.1 Descriptive statistics

Demographic and clinical characteristics of patients who developed OIWS will be compared to those who did not. Categorical variables will be presented as proportions. For continuous variables, means and standard deviations will be computed for normal distributions whereas medians (interquartile range) will be used for non-normal distributions.

For the primary outcome, episodes will be compared between the withdrawal positive (W+) group and the withdrawal negative (W-) group. Every day on which the DSM-5 is positive is equivalent to an episode of withdrawal, whereas a negative DSM-5 counts as an episode in which no withdrawal was observed. Patients who are positive for at least one episode of withdrawal make up the W+ group, whereas those who did not have a single episode of withdrawal make up the W- group, thus eliminating crossover. If a single patient experiences multiple days of withdrawal, s/he will account for multiple episodes in the study. Signs and symptoms will be tallied per episode and compared between the two groups. The results will be presented as proportions (i.e. incidence of symptom per total episodes). In the event of a discordant inter-rater evaluation, only the positive result will be taken into account.

For the secondary outcome, serum cortisol levels and changes in serum cortisol levels are continuous variables and therefore descriptive statistics will be used as stated above, depending on the distribution.

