Appendix II. Study procedure

Appendix III. Dependent variables: signs and symptoms of OIWS (4, 15, 19, 20, 24)

Category	Signs and symptoms	Definition	Type of variable
Central nervous system symptoms	Agitation	During ICU hospitalization: Highest RASS score recorded in the previous 24h ^a according to nurse assessment ^{b, c}	Qualitative ordinal
		RASS -5 to 0, 1 (restlessness) or ≥ 2 (agitation)	Qualitative ordinal
		After ICU transfer to another ward: Agitated Behavior Scale (ABS) score during evaluation ≤ 21: No agitation; ≥ 22: agitation	Qualitative ordinal
	Anxiety	According to patient or nurse assessment in the previous 24h	Qualitative nominal (dichotomous)
	Dysphoria	According to physician DSM-5 evaluation	Qualitative nominal (dichotomous)
	Fever	Highest temperature value (°C) according to nurse assessment in the previous 24h	Quantitative continuous
		Temperature ≥ 38.3 degrees in the previous 24h	Qualitative nominal (dichotomous)
	Hallucinations	Patient seems to see, hear or feel things that are not there in the previous 24h, according to patient or nurse assessment	Qualitative nominal (dichotomous)
	Insomnia/sleep disturbance	Number of hours of sleep/night between 10PM and 6AM the night before evaluation according to nurse assessment	Quantitative discrete
		Lack of sleep defined as less than 4 hours of continuous sleep between 10PM and 6AM	Qualitative nominal (dichotomous)
	Startle to stimulus	Startle occurs when patient is stimulated verbally or by light touch during evaluation	Qualitative nominal (dichotomous)
	Time to regain calm post-stimulus	Time (minutes) needed to regain calm post-stimulus	Quantitative continuous
		Normal: < 2 min; Increased: 2 to 5 min; High: > 5 min	Qualitative ordinal
	Seizure	Presence not explained by metabolic disturbances or history of seizures in the previous 24h according to medical chart	Qualitative nominal (dichotomous)
Tremor	Presence of trembling, involuntary sustained rhythmic movements of hands and/or	Qualitative nominal (dichotomous)	

		feet during evaluation or according to nurse assessment in the previous 24h	
	Pupil size	Size (mm) according to nurse assessment in the previous 24h ≤ 2 mm, > 2 mm	Quantitative continuous Quantitative discrete (dichotomous)
	Yawning	Number of yawns in the previous 24h according to nurse assessment If ≥ 2 yawns observed during evaluation or in the previous 24h according to nurse assessment	Quantitative continuous Quantitative discrete (dichotomous)

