Cardiac symptoms	Hypertension	Highest Systolic blood pressure (mmHg) according to nurse assessment in the previous 24h	Quantitative continuous
		Highest MAP (mmHg) according to nurse assessment in the previous 24h	Quantitative continuous
	Tachycardia	Highest HR in the previous 24h	Quantitative continuous
		Lowest heart rate in previous 24h	Quantitative continuous
		Is patient on a beta-blocker ; Yes or No	Qualitative nominal (dichotomous)
Respiratory symptoms	Frequent suction	Number of times patient required endotracheal suctioning in the previous 24h according to nurse assessment	Quantitative continuous
	Lacrimation	Presence during evaluation or according to nurse assessment in the previous 24h	Qualitative nominal
	Rhinorrhea	Presence during evaluation or according to nurse assessment in the previous 24h	Qualitative nominal (dichotomous)
	Sneezing	Number of sneeze observed during evaluation or according to nurse assessment in the previous 24h	Quantitative continuous
		If more than 1 sneeze observed during evaluation or according to nurse assessment in the previous 24h	Qualitative nominal (dichotomous)
	Significant dyspnea	Highest respiratory rate (RR) recorded in the previous 24h according to nurse assessment	Quantitative continuous
		Lowest respiratory rate (RR) recorded in the previous 24h	Quantitative continuous

		according to nurse assessment	
Gastrointestinal symptoms	Diarrhea	Presence of ≥ 3 BMs (loose/watery stools), in past 24 hours according to nurse assessment	Qualitative nominal (dichotomous)
		Number of BM in the previous 24h according to nurse assessment	Quantitative continuous
		Rectal tube required (yes or no)	Qualitative nominal (dichotomous)
	Feeding intolerance (gastric residuals)	Present if nurse discontinued or decreased enteral feeding during previous 24h due to gastric residuals of more than 500 mL according to nurse assessment	Qualitative nominal (dichotomous)
	Nausea	Presence during previous 24h according to patient, nurse assessment or use of antiemetic medications such as dimenhydrinate and ondansetron (indication to validate with nurse when necessary)	Qualitative nominal (dichotomous)
Vomiting	Presence or absence of vomiting episode(s) or retching or gagging in the previous 24h according to nurse assessment	Qualitative nominal (dichotomous)	

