Dermatologic symptoms	Mottling	Presence of violaceous marbled discoloration of the skin during evaluation or according to nurse assessment in the previous 24h	Qualitative nominal (dichotomous)
	Piloerection	Presence during evaluation or according to nurse assessment in the previous 24h	Qualitative nominal (dichotomous)
	Sweating	Presence without apparent reason (not caused by room temperature) during evaluation or according to nurse assessment in the previous 24h	Qualitative nominal (dichotomous)
Musculoskeletal symptoms	Bone, joint or muscle aches	Presence during evaluation or according to nurse assessment in the previous 24h	Qualitative nominal (dichotomous)
	Muscle cramps	Presence during evaluation or according to nurse assessment in the previous 24h	Qualitative nominal (dichotomous)
	Muscle tone	Presence during evaluation or according to nurse assessment in the previous 24h	Qualitative nominal (dichotomous)

		(e.g. clenching wrists and toes, hunched shoulders, abnormal tense position of head, arm or legs)	
	Uncoordinated/ repetitive movement	Presence of involuntary movements of arm and/or legs, muscle twitches, during evaluation or according to nurse assessment in the previous 24h	Qualitative nominal (dichotomous)

^a Previous 24h designate the interval between midnight of the previous day and midnight of the day on which evaluation of the signs and symptoms occurs. A fixed time frame was chosen to standardize collection of signs and symptoms.

^b Nurse assessment comprises written (i.e. notes in medical chart or patient flow sheet) and/or verbal communication.

^c On the day of transfer, patients will be evaluated from midnight of the previous day until time of evaluation. Following transfer to ward, patients will be evaluated from midnight of the current day to time of evaluation.

Appendix IV. Diagnostic and Statistical Manual of Mental Diagnosis-V (DSM-5): “Opioid Withdrawal” criteria.

Diagnostic criteria:

A. Presence of either of the following;

1. Cessation of (or reduction in) opioid use that has been heavy and prolonged (i.e., several weeks or longer).
2. Administration of an opioid antagonist after a period of opioid use.

B. Three (or more) of the following developing within minutes to several days after

1. Dysphoric mood.
2. Nausea or vomiting.
3. Muscle aches.
4. Lacrimation or rhinorrhea.
5. Pupillary dilation, piloerection, or sweating.
6. Yawning.
7. Fever.
8. Insomnia.

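### Twelve of the 30 Appendix III signs are also DSM-5 criterion B signs that help define W+ and W-, so part of their W+ v W- difference is built in

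*Combined protocol and SAP*

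**What the plan says.** The primary objective (section 3) is to identify specific signs and symptoms of opioid-associated iatrogenic withdrawal syndrome (OIWS). Section 4.1 looks ahead to a bedside screening tool.

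- **Outcome signs.** Section 4.4.1 says they are recorded "According to daily evaluation by investigator after an episode of opioid weaning has begun" and refers to Appendix III for the list.
- **Grouping.** Section 4.4.1 determines OIWS "According to DSM-5 evaluation completed daily by physician after an episode of opioid weaning has begun". In section 5.1.1 each DSM-5 positive day is an episode of withdrawal, and "Patients who are positive for at least one episode of withdrawal make up the W+ group".
- **Case definition.** Criterion B in Appendix IV asks for "Three (or more) of the following developing within minutes to several days after" and lists eight items. Criteria A, C and D must also be met.
- **Comparison.** "Signs and symptoms will be tallied per episode and compared between the two groups", and "The results will be presented as proportions (i.e. incidence of symptom per total episodes").
- **Dysphoria.** Its Appendix III row gives the source as "According to physician DSM-5 evaluation".

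Investigators are blinded to the DSM-5 results (sections 4.1, 4.5 and 6.1). Neither section 5.1 nor section 6.2 says that the outcome list and the case definition share signs.

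**The concern.** A day can be positive only if at least three criterion B items are present. Selecting positive days therefore raises the frequency of the signs in those items, whether or not they are good markers of withdrawal. A sign outside criterion B gets no such direct lift. If all 30 signs are set side by side, the criterion B signs tend to look more discriminating than they are, and they could be carried into a screening tool on evidence that the DSM-5 definition partly supplied.

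For dysphoria the problem is complete: one physician record supplies both the sign and part of the diagnosis. This also conflicts with section 4.4.1, which assigns outcome signs to the investigator. It resembles the weakness that section 2 (Assessment tools) finds in the paediatric validation studies, where one rater scored both the tool and withdrawal severity.

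**Working it through.** **Step 1. Count the overlap.** The plan gives no count. Appendix III by category: 12 central nervous system + 2 cardiac + 5 respiratory + 4 gastrointestinal + 3 dermatologic + 4 musculoskeletal = 30 signs. Matched to the criterion B items in Appendix IV:

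| Criterion B item | Appendix III signs | Number |
|---|---|---|
| 1 | dysphoria | 1 |
| 2 | nausea, vomiting | 2 |
| 3 | bone, joint or muscle aches | 1 |
| 4 | lacrimation, rhinorrhea | 2 |
| 5 | pupil size, piloerection, sweating | 3 |
| 6 | yawning | 1 |
| 7 | fever | 1 |
| 8 | insomnia | 1 |
| Total | | 12 |

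So 12/30 = 40% are shared and 18 are not.

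**Step 2. Null model: signs unrelated to withdrawal.** All inputs are assumptions. There are 12 independent signs, each present on a share p of days. A criterion with m signs is met with probability 1 - (1-p)^m. A random share pi of criterion-B-positive days passes criteria A, C and D. Each patient has n days. Write PB = P(at least 3 of 8 criteria), q = 1 - pi x PB, and J = p x P(at least 2 of the other 7).

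- Share on positive days: J/PB
- Share on W- patients' days: (p - pi x J)/q
- Share on all days of W+ patients: (p - (p - pi x J) x q^(n-1))/(1 - q^n)

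Base case p = 0.10, pi = 0.5, n = 5, for a sign that is a criterion by itself:

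- PB = 0.0916, q = 0.9542, J = 0.10 x 0.2828 = 0.0283
- Positive days: 0.0283/0.0916 = 30.9%
- W- days: (0.10 - 0.0141)/0.9542 = 9.0%
- All W+ days: (0.10 - 0.0859 x 0.8291)/0.2089 = 13.8%
- W+ patients: 1 - 0.9542^5 = 20.9%
- Gap: 21.9 points (positive days) or 4.8 points (all W+ days)

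The grid was p 0.05-0.20 (step 0.01), pi 0.25-1 (step 0.05) and n 3-10. Only the 278 settings with 12-22% of patients W+ were kept, around the 16.7% incidence cited in section 1. Gaps in points:

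| Signs in the criterion | Positive days | All W+ days |
|---|---|---|
| 1 | 16.9-25.3 | 2.4-8.4 |
| 2 | 13.5-20.6 | 1.9-6.8 |
| 3 | 10.6-16.8 | 1.5-5.5 |

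A sign outside criterion B has a gap of zero in this model.

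**Step 3. Criterion D applied perfectly.** Every positive day is now true withdrawal, and each sign has prevalence p1 on withdrawal days. The share on positive days is p1 x P(at least 2 of the other 7)/P(at least 3 of 8). At p1 = 0.20 this is 0.20 x 0.6497/0.3857 = 33.7%. A sign outside criterion B stays at p1.

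| p1 | One-sign | Two-sign | Three-sign | Lift, one-sign (points) |
|---|---|---|---|---|
| 20% | 33.7% | 30.9% | 28.4% | 14 |
| 30% | 37.9% | 36.1% | 34.5% | 8 |
| 40% | 43.8% | 42.9% | 41.9% | 4 |
| 50% | 51.4% | 51.0% | 50.6% | 1 |

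If all days of W+ patients count, a simulation (assumed background prevalence 10%, 5 days per patient, 5-10% withdrawal days, p1 20-40%) gave a lift of about 1-3 points.

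**Step 4. Separate raters.** The figures above apply in full only to dysphoria. For the other 11 signs, suppose the investigator and the physician record a sign equally often and agree with kappa k. The gap in the investigator's record is then k times the gap in the physician's. Over an assumed k of 0.3-1.0, a gap of 21.9 points becomes 21.9 x 0.3 = 6.6 up to 21.9 points. The documents give no value: the kappa in section 5.1.2 is between physicians and concerns the overall diagnosis.

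**The case against.** The strongest reply is that the study is descriptive. The research question asks only what the signs are, section 5.1.2 plans no test on them, and section 6.2 says no statistically significant associations can be made. On that reading *specific* may mean no more than *particular*, and frequency is the main result. The frequency of the 12 signs is indeed valid and useful, since section 2 says it is unclear whether all of them occur in opioid-naive patients. But section 5.1.1 does plan a W+ v W- comparison, and the built-in gap appears in descriptive proportions without any test.

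Second, any symptom-based reference standard shares signs with its syndrome, and section 4.6 says that nothing validated exists for adult ICU patients. That stands: the point is not to replace DSM-5 but to report the overlap. Blinding limits observer bias, but both raters see the same patient, so days are still selected on the same signs.

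Third, the null model is towards the high end, because criterion D exists to reject such days. That is fair, and step 3 is the counterweight. With about 8 W+ patients (16.7% of 50 = 8.35), a lift of 1-3 points under all-days counting would be lost in noise. The concern is material mainly if W+ is tallied on positive days, and section 5.1.1 does not say which days count.

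Fourth, the 12/18 split is not perfectly clean. Appendix III divides pupil size at 2 mm while criterion B names dilation, so a strict match gives 11. Criterion C's distress requirement may also let anxiety or agitation influence the diagnosis. Neither changes the direction.

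**Conclusion.** The concern holds. For dysphoria the comparison is circular on the face of the text, and no model is needed. For the other 11 shared signs, part of the W+ v W- difference is supplied by the case definition, so it is not independent evidence of specificity. The 18 other signs get no such direct lift.

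Confidence is high on direction only. The size depends on assumed prevalences, independence of signs, how strictly criterion D is applied, rater agreement, and which days of W+ patients count. Over the ranges examined for a one-sign criterion, before any rater disagreement, it runs from about 1 to 25 points. This should be corrected. It does not undermine the study's value as a description of how often signs occur.

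**What to change.** In section 5.1.1:

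1. Drop dysphoria from the W+ v W- comparison and report only its frequency on the DSM-5 forms.
2. Report the other 11 criterion B signs in a separate block labelled as components of the case definition. Describe how often they occur, and do not treat their W+/W- difference as independent evidence of specificity.
3. Rest claims about discriminating signs beyond the DSM-5 list on the remaining 18. Of these, 12 are yes/no and 2 are ordered (agitation, time to regain calm). The other 4 (hypertension, tachycardia, suction, dyspnea) have no present/absent cut-off in Appendix III; the hypertension row, for example, records "Highest Systolic blood pressure (mmHg) according to nurse assessment in the previous 24h". These 4 cannot be shown as proportions and should be compared as continuous values.

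State the overlap in section 6.2.

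The cost is in analysis and reporting only. Fewer signs support the specificity conclusion (14 categorical and 4 continuous), and dysphoria gets no comparison. Re-classifying days with one criterion item left out is optional and exploratory. It needs item-level DSM-5 forms, loses 23-50% of positive days in the null base case when a whole item is removed, cannot recompute criteria C and D, and adds little with about 8 W+ patients.

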Appendix XII. Critical-Care Pain Observation Tool (CPOT) developed by Gelinas et al. .35
Appendix XIII. Numeric Rating Scale (NRS).....36

Abbreviation list

ICU	Intensive care unit
IWS	Iatrogenic withdrawal syndrome
MGH	Montreal General Hospital
MUHC	McGill University Health Centre
OIWS	Opioid-associated iatrogenic withdrawal syndrome
PICU	Pediatric intensive care unit
RVH	Royal Victoria Hospital

1. Introduction

Adult medical, surgical and trauma intensive care unit (ICU) patients routinely experience pain, agitation, delirium and anxiety (1). Opioids and benzodiazepines are the primary medications to relieve pain, facilitate mechanical ventilation and decrease physiological and psychological stress in the critically ill (1). In a prospective, observational study in 51 Canadian ICUs, 92% of patients received opioids and sedatives at least once during mechanical ventilation (2). Upon repeated and prolonged administration, opioid tolerance may develop as a result of receptor desensitization and upregulation of excitatory intracellular pathways (2, 3). When these drugs are abruptly discontinued or rapidly tapered, patients may develop a cluster of signs and symptoms known as the acute iatrogenic withdrawal syndrome (IWS). While this phenomenon is well described in the pediatric critical care population, there is a paucity of data in critically ill adults (4-7). IWS has been associated with negative clinical outcomes such as increased length of hospital stays, prolonged duration of mechanical ventilation and higher cost of hospitalization (4-7).

In one prospective, observational study, the reported incidence of IWS in the adult ICU population was 16.7% (8). In prospective studies done in the pediatric ICU (PICU), observed incidence was 7.5 to 100% (9). Two assessment tools have been validated in children: The Withdrawal Assessment Tool-Version 1 (WAT-1) and the Sophia Observation Withdrawal Symptoms-scale (SOS) (10). No such tool currently exists in the adult ICU (9).

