The literature on opioid dependence has consistently demonstrated elevated levels of cortisol (12, 25-38) and catecholamines (12, 39-43) during the acute withdrawal phase. Human and animal

models postulate that long-term use of opioids induces hypoadrenalism through impairment of the hypothalamic-pituitary-adrenal (HPA) axis. Opioid withdrawal leads to marked elevations of cortisol as a result of excess ACTH secretion (26, 32, 35). This HPA activation persists following normalization of the adrenergic system, which led some authors to conclude that cortisol is a more sensitive indicator of opioid withdrawal than catecholamines (30, 32). A small study by Higgins et al. on 5 non-dependent subjects assessed acute opioid withdrawal after a single dose of morphine and observed a dose-dependent increase in cortisol levels when subjects were subsequently injected with naloxone (28). Despite the clinical relevance, several limitations reduce the applicability of those results to our study population, mainly the selection of opioid-dependent subjects and rapid induction of withdrawal – through injection of naloxone or abrupt cessation of opioid with support medications such as alpha₂-agonists. Since our subjects are mostly opioid-naive prior to hospitalization and will be gradually weaned off their opioids, the magnitude of increase in cortisol levels will likely be lower.

As for catecholamines, serum epinephrine and norepinephrine appear to increase rapidly following opioid withdrawal in numerous animal and human studies (12, 39-43). However, in contrast with cortisol, catecholamine levels decrease shortly following acute withdrawal. In a study of subjects undergoing rapid opioid detoxification, catecholamine levels peaked two hours following naloxone administration (12). A gradual opioid weaning as often seen in clinical practice is unlikely to be recognized through measurement of serum catecholamines.

3. Research objectives

Research question

What are the signs and symptoms of opioid-associated iatrogenic withdrawal syndrome (OIWS) in the adult ICU population?

Primary objective

To identify specific signs and symptoms of OIWS in mechanically ventilated adult ICU patients receiving at least 72 hours of regular opioids at the Montreal General Hospital (MGH) and the Royal Victoria Hospital (RVH) from February to October 2018

Secondary objective

To determine if the presence of OIWS is associated with an increase in serum cortisol.

4. Methods

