5.2 Sample size

Based on our experience with the WAAICUP studies, 88 patients were eligible to participate in the study in an 8-month period, of which around 50 consented (22). We thus aim to recruit 50 patients based on the feasibility of these previous studies.

6. Advantages and limitations

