6.2 Limitations

The study is susceptible to several limitations, most of them due to study design. Due to lack of randomization, the study is subject to confounding. A notable covariate is the concomitant administration of benzodiazepines, which is difficult to control for since ICU patients frequently receive both opioids and benzodiazepines, and there is significant overlap in their respective withdrawal symptoms. However, administration of benzodiazepines will be noted during daily evaluations. The study is also susceptible to the "clinical trial effect" bias, since the attending physicians are not blinded to patient enrollment in the study and may modify their management consequently. To control for observer bias, pre-tested standardized data collection forms will be used, but it does not eliminate it completely, as evaluations will be performed by different investigators.

Since the sample size was determined on the basis of feasibility rather than statistical power, no statistically significant associations can be made. Statistical analyses will thus be predominantly descriptive in nature.

The exclusion of patients with severe or moderate traumatic brain injury requiring ICP monitoring and osmotherapy reduces external validity. These patients are important consumers of opioids and are therefore at risk of developing OIWS. However, their clinical condition would make the adequate assessment of OIWS impossible.

7. Relevance of study

To our knowledge, this is the first prospective study that aims to describe the clinical presentation of OIWS in the adult ICU setting with a standardized approach, fulfilling an identified research gap (71). As mentioned, OIWS is a clinical entity associated with negative outcomes that is poorly understood in critically ill adults because of diagnostic challenges. With a more accurate description of the clinical presentation, it would be possible to develop reliable screening tools to identify patients most at risk of OIWS and to sensitize the clinician to adopt appropriate measures in their management. An accurate description of the clinical presentation of OIWS is the first step in a series of research advances aimed at correctly recognizing and managing OIWS in adult ICU patients.

8. Ethical considerations and patient consent

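### Section 5.1.1 compares signs between W+ and W- as bare per-episode proportions, with no measure of precision, although only about 8 W+ patients are expected

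*Combined protocol and SAP*

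**What the plan says.** - Section 3 (Primary objective): "To identify specific signs and symptoms of OIWS in mechanically ventilated adult ICU patients". Section 4.1 says this is done in the prospect of a validated bedside screening tool.
- Section 5.1.1 sets the groups by patient: "Patients who are positive for at least one episode of withdrawal make up the W+ group". The unit counted is the day: "If a single patient experiences multiple days of withdrawal, s/he will account for multiple episodes in the study". The comparison is "Signs and symptoms will be tallied per episode and compared between the two groups", shown as proportions of total episodes.
- Section 5.1.2 (Statistical inference) covers Cohen's kappa and the cortisol comparison only. Nothing there applies to the signs.
- Section 5.2: "We thus aim to recruit 50 patients based on the feasibility of these previous studies".
- Section 6.2 says that the sample size rests on feasibility, so no statistically significant associations can be made, and adds: "Statistical analyses will thus be predominantly descriptive in nature".
- Appendix III lists the signs. Appendix IV gives the DSM-5 criteria that define a withdrawal-positive day.

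**The concern.** The secondary outcome gets a test and the reliability check gets a kappa, while the primary comparison gets neither an interval nor any other indication of how far a proportion could move by chance. With very few W+ patients, each contributing several correlated days, a table of percentages will look firmer than it is. A reader who sees 50% against 25% per episode cannot tell that the first figure may rest on a handful of people.

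The table is also meant to inform later work on a screening tool. When many signs are compared in a small group, some sizeable differences are expected by chance, and the planned output gives no means of judging which could be of that kind.

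**Working it through.** **The plan's own figure.** There is no power or precision formula to reproduce. Section 5.2 reports that "88 patients were eligible to participate in the study in an 8-month period, of which around 50 consented" (50/88 = 57%) and carries the 50 forward as the target.

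**Expected W+ patients.** N = 50 (section 5.2) and incidence 16.7% (Introduction; the one prospective adult ICU study cited): 50 × 0.167 = 8.35, so about 8 W+ and 42 W-. The 95% binomial range is 4 to 14. Section 2 also cites retrospective incidences from 19.7% upwards (50 × 0.197 = 9.85), so the count could be higher.

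**Precision at that size.** Clopper-Pearson 95% intervals, one observation per patient:
- 4 of 8 W+ patients: 50% (16% to 84%)
- 2 of 8 W+ patients: 25% (3% to 65%)

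**How many signs.** Count in Appendix III: central nervous system 12 + cardiac 2 + respiratory 5 + gastrointestinal 4 + skin 3 + musculoskeletal 4 = 30.
- Hypertension, tachycardia, frequent suction and dyspnea have only continuous or count definitions: 30 − 4 = 26 signs with a defined proportion.
- Twelve signs feed criterion B in Appendix IV: dysphoria, nausea, vomiting, aches, lacrimation, rhinorrhea, pupil size, piloerection, sweating, yawning, fever and insomnia. They are tied to the W+ label by construction, so a no-association benchmark means something for at most 30 − 12 = 18 signs.
- None of the four continuous signs is among the twelve, so 18 − 4 = 14 signs are both categorical and outside criterion B.

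**Chance benchmark.** The documents give no sign prevalence, days per patient or within-patient correlation (ICC). Assumed: 8 v 42 patients; independent signs; the same true prevalence in both groups, uniform on 10% to 50%; either one observation per patient, or day-level data with geometric day counts (mean 3 in W+, 5 in W-, cap 14) and a beta-binomial patient effect. 3,000 simulations per setting. Each cell gives the mean largest W+ minus W- difference, then the mean number of signs above +15 points:

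| Signs compared | One obs. per patient | Days, ICC 0.2 | Days, ICC 0.4 |
|---|---|---|---|
| 30 | 37 points; 5.6 | 28; 3.8 | 33; 4.9 |
| 18 (outside criterion B) | 32; 3.3 | 25; 2.3 | 30; 3.0 |
| 14 (also categorical) | 31; 2.7 | 23; 1.8 | 28; 2.3 |

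A between-sign correlation of 0.2 lowers the 14-sign maximum slightly, to 22 to 29 points.

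**Sensitivity.** Over wider choices (prevalence 10% to 50%, ICC 0 to 0.7, 2 to 4 W+ and 4 to 5 W- days per patient or one observation each, 18 or 30 signs), the median largest absolute difference with 8 W+ patients runs from about 18 to 42 points. The W+ count also matters: with 30 signs, 3 W+ and 5 W- days per patient, ICC 0.5 and prevalence 30%, it is 42 points with 4 W+ patients, 32 with 8 and 26 with 14.

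**The case against.** The strongest reply is that the protocol is open about its limits. It calls the design descriptive, puts this comparison under descriptive statistics, sets N on feasibility and disclaims significant associations. Section 7 presents the study as the first of several steps, so any tool lies further off. All of that stands, and it answers a complaint about power. It does not answer this point: a descriptive estimate still has a precision, and the plan reports none.

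Three stronger readings are tempting, and the documents do not support them.

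- A reader might infer that the largest chance difference will be 30 to 37 points across 30 pairs of proportions. That rests on unstated prevalences and correlations. Its upper end comes from one observation per patient, whereas the plan counts episodes. Only 26 signs have a proportion, and 12 of the 30 cannot be unrelated to a label they help define.
- A reader might infer that the study would name false signs. The protocol contains no ranking rule, no cut-off and no statement that the largest excesses will be chosen; +15 points is only a yardstick used here.
- A reader might infer that a sign should count as identified only above a permutation threshold for the largest of 30 differences. That would mix in the circular DSM-5 signs and set a very high bar. In the 30-sign null simulations the 95th percentile of the maximum is 48 points (days, ICC 0.4) to 54 points (one observation per patient). Take a sign truly present in 60% of W+ and 30% of W- patients: the difference is 0.30, with standard error √(0.24/8 + 0.21/42) = 0.187. It would exceed 48 points about 17 to 18% of the time and 54 points about 10%. Section 5.1.1 also does not settle whether a W+ patient's DSM-5-negative days count, and a permutation needs that.

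**Conclusion.** The point holds in a limited form. The primary comparison has no measure of precision, although the objective is to identify specific signs, days are clustered within patients, and about 8 W+ patients are expected (range 4 to 14, taking the cited 16.7% as the true rate). The interval of 16% to 84% for 4 of 8 patients needs no further assumption beyond one observation per patient.

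The chance benchmark (a largest W+ excess averaging about 23 to 31 points among the 14 categorical signs outside criterion B, with about two above +15) depends on the assumed prevalence, day counts, correlation and independence of signs. It illustrates the problem and is not a forecast; 18 to 42 points is the range over wider assumptions and sign counts. The point is a cheap improvement and does not undermine the study.

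**What to change.** Amend section 5.1.1 as follows.

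1. Report each W+ minus W- difference with a 95% interval that treats the patient as the cluster, and note that intervals resting on about 8 W+ patients are approximate. A patient-level bootstrap is one option, but with so few W+ patients it carries the same caution. For the four signs recorded only as continuous values or counts, give the corresponding difference with the same kind of interval.
2. Present the 12 signs that feed DSM-5 criterion B separately from the other 18, and say that the first set is linked to the group label by definition.
3. Describe the results as candidate, hypothesis-generating signs, in line with section 6.2.
4. Optional: state which days of a W+ patient count, then print a reference value for the largest difference among the signs outside criterion B, obtained by permuting the W+/W- label among patients. Give it as context, not as a pass/fail threshold.

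Cost: some wording and a little more analysis, with no extra patients, visits or data. The downside is wide intervals, which will make the sign list look less definite.
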